7.6 Adjuvant Whole Breast Irradiation (WBI)

Patients receiving BCT should receive adjuvant whole breast radiation with a boost to the lumpectomy bed of each site of disease. The boost will be limited to two quadrants of the breast only. **Note:** Patients who cannot or do not receive boost radiation are ineligible and must discontinue the study. The end of study information should be collected and the patient referred to clinical care. Addition of nodal radiation fields will be at the discretion of the treating radiation oncologist.

Patients may receive WBI at an institution other than the enrolling institution. Note that the enrolling institution is responsible for the correct performance of WBI at the other institution and the reporting of all study data. The institution performing WBI must follow all requirements for WBI listed in the protocol, including regulatory requirements such as submission of an RTFI form to CTSU and submission of treatment plans to IROC Rhode Island (QARC).

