7.61 Treatment Planning/Delivery

- 7.611 Three-dimensional CT-based treatment planning is required.
- 7.612 Heterogeneity corrections are required.
- 7.613a Intensity modulated radiotherapy (IMRT) with inverse planning is allowed.
- 7.613b Breath hold technique is allowed
- 7.614 Optimization with forward planning is allowed.
- 7.615 Linear accelerators with minimal photon energies of 6MV and electron energies of 6eMEV-20eMEV are required.
- 7.616 Either electrons or photons may be used for boost treatment.
- 7.617 Boost treatment to each lumpectomy cavity is required.
Note: Patients who cannot or do not receive a boost are ineligible and must discontinue the study. The end of study information should be collected and the patient referred to clinical care.
- 7.618 Boost with intraoperative radiotherapy or HDR brachytherapy is not allowed.
- 7.619 Hypofractionation is not allowed.

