13.2 Conditions Requiring Study Termination

Patients who convert to a mastectomy for any reason within a year of initial surgery will go to the observation phase of the study. All data and forms prior to and up to mastectomy must be submitted. Tissue from the mastectomy should be submitted if possible. Patients will be followed for survival yearly for 5 years after treatment discontinuation.

Patients found to have any of the following:

- those with persistent positive margins who decline mastectomy;
- the dose constraint is not met (≤ 10 weeks of initial attempt of WBI planning in patients not receiving adjuvant chemotherapy, or ≤ 8 weeks after completion of chemotherapy for those patients receiving chemotherapy)

will have participation in the study terminated. The on-study material, surgery forms, pathology forms and the End of Active Treatment/Cancel Notification Form must be submitted. No further data submission is needed.

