13.5 Definition of Ineligible

A patient is deemed *ineligible* by the data center if, after registration, it is determined that at the time of registration, the patient did not satisfy each and every eligibility criteria for

study entry.

- If the patient did undergo surgery with/without radiation, submit all treatment/intervention forms and the Off Treatment/Cancel Notification Form.
- If the patient did not undergo surgery, submit on-study material and the Off Treatment/Cancel Notification Form. No further data submission is necessary.

Note: If, after a site has registered a patient into the study, the site becomes aware of information that questions the patient's eligibility for the study, the site should contact the QAS/Data Manager at the telephone number and/or email address listed on the Protocol Resources page of the protocol.

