16.62 Conversion to Mastectomy

The conversion rate to mastectomy secondary to persistent positive margins; poor cosmesis within the first year of attempting BCS; or inability to satisfy the radiation dose constraints on the boost to the lumpectomy bed of each site of disease

All eligible patients who have initiated surgery will be included in the analysis of conversion to mastectomy. A 95 % binomial confidence interval will be constructed for the percentage of patients who converted to mastectomy. Logistic regression analysis will be used to assess whether the likelihood of conversion to mastectomy differed with respect to patient and/or disease characteristics.

An interim efficacy analysis will not be performed; final analysis will be performed at year 7 after patients have at least 5 years of follow-up.

Patients enrolled subsequent to surgery will be excluded from this analysis.

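### Section 13.2 can close out a woman who fails the radiation dose constraint before a mastectomy that the conversion endpoint counts, and its 10-week limit contradicts 7.634

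*Combined protocol and SAP*

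**What the plan says.** The conversion endpoint (2.21, 16.2, 16.62) counts mastectomies done for persistent positive margins, for poor cosmesis in the first year, or because the boost could not be planned within the dose limits. Section 16.62 sets the analysis population: "All eligible patients who have initiated surgery will be included in the analysis of conversion to mastectomy". Women registered after surgery are left out.

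Sections 7.622 and 7.634 take a woman whose plan fails the constraint off protocol therapy, recommend mastectomy, and refer to 13.2. That section has two rules.

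- Paragraph 1: "Patients who convert to a mastectomy for any reason within a year of initial surgery will go to the observation phase of the study". Data up to the mastectomy must be sent in.
- Paragraph 2 terminates two groups. One is "those with persistent positive margins who decline mastectomy". The other is women whose dose constraint is not met, with no such limit. For both, once the on-study, surgery, pathology and end-of-treatment forms are in, "No further data submission is needed".

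For women without chemotherapy, the time limit in the dose-constraint bullet is "10 weeks of initial attempt of WBI planning in patients not receiving adjuvant chemotherapy". Section 7.634 counts its 10 weeks from the last surgery.

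On eligibility, the notes in 7.6 and 13.3 read "Patients who cannot or do not receive boost radiation are ineligible and must discontinue the study", and 7.617 reads "Patients who cannot or do not receive a boost are ineligible and must discontinue the study". Section 13.5 uses the same term for a case where "at the time of registration, the patient did not satisfy each and every eligibility criteria".

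**The concern.** The two rules in 13.2 overlap for a woman who fails the constraint and then has the recommended mastectomy, and nothing says which prevails. Order in time makes this matter. On the day the constraint fails she has not yet converted, so only the termination bullet clearly describes her. A site that acts on it sends the closing forms and need not report an operation weeks later. That operation is an event the conversion endpoint is defined to capture, so the reported rate could be too low.

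A second group is affected differently. A woman who fails the constraint and keeps her breast has not converted. If her margins are negative and her lesions were not one contiguous area, she appears to meet the description of the primary analysis set in 16.2 and 16.61. Section 13.2 nevertheless ends her data submission, so a later local recurrence would not have to be reported.

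The two clocks give sites different dates for the same decision. The boost notes use the word ineligible for something that happens after registration, which 13.5 does not allow, and 16.62 analyses only eligible women.

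**Working it through.** **Plan's own figures.** The conversion stopping rule in 16.51 gives a lower 95% bound of 25.7% for 35 of 100. The exact binomial bound is the 2.5th percentile of Beta(35, 66) = 25.73%, which agrees. That rule counts only margins or cosmesis within 6 months, so lost dose-constraint mastectomies do not enter it. Section 16.3 says 8 recurrences in 200 keep the upper bound below 8%. The exact Poisson bound, chi-square(0.975; 2 × 8 + 2)/2 divided by 200, is 7.88%, which agrees. Nine recurrences give 8.54%.

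**Unrecorded conversions.** Let n be the conversion analysis set, x the true conversions and k those not recorded. The documents give none of these, except that n cannot exceed the accrual target of 265 (16.3) if accrual stops there. The reported rate is (x − k)/n, so each loss costs 1/n.

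| Assumed n | Loss per unrecorded conversion (percentage points) |
|---|---|
| 100 | 1.00 |
| 150 | 0.67 |
| 200 | 0.50 |
| 265 | 0.38 |

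Illustration with assumed n = 200 and x = 20 (10.0%):

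- k = 1: 19/200 = 9.5%
- k = 3: 17/200 = 8.5%
- k = 5: 15/200 = 7.5%

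**If the boost notes removed women from the set.** Let m women be dropped, of whom c converted. The rate becomes (x − c)/(n − m). With the same n and x:

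- m = 1, c = 1: 19/199 = 9.55%, lower
- m = 1, c = 0: 20/199 = 10.05%, higher
- m = 10, c = 1: 19/190 = 10.0%, unchanged

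The direction depends on whether the dropped women converted more or less often than the rest.

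**Women who decline mastectomy.** Their number is not given, so no effect on the recurrence estimate can be computed. The two Poisson bounds above show only that, at the edge of the 16.3 criterion, a single unreported recurrence could decide on which side of 8% the bound falls.

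**Clock, no chemotherapy.** Let p be the week of first planning after the last surgery. Section 7.631 allows 0 ≤ p ≤ 6. The 13.2 limit is week p + 10, that is week 10 to week 16. The 7.634 limit is week 10. The gap is p, or 0 to 6 weeks. For p above 2 the 13.2 limit falls after week 12, the latest radiation start in the item numbered 7.365.

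**Clock, chemotherapy.** Sections 7.622 and 13.2 both give 8 weeks after chemotherapy ends. The gap is 0.

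**The case against.** The best defence is that paragraph 1 already covers converters whatever their reason. Sections 7.2, 7.622 and 7.634 all send the reader to 13.2 in the context of mastectomy, so paragraph 1 is the natural rule. Paragraph 2 also still asks for surgery and pathology forms, and the surgery phase in 18.2 runs to 30 days after the final operation, which could take in a prompt mastectomy. Much of this stands and makes loss less likely. It does not remove the overlap: the margin bullet has the limit, the bullet beside it does not, and nothing requires a form for an operation after termination.

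A reader might infer that the boost notes strike dose-constraint converters from 16.62 and so bias the rate downward. The documents do not support that. The same reading would also remove women converted for positive margins before radiation, since they receive no boost either, and that would empty much of the endpoint. In 7.6 the note follows text about women receiving breast conservation. It also takes an inference to say that a woman who misses the cumulative limit cannot be boosted, since 7.663 and 7.69b3 accept 50% to 60% of the breast volume above 60 Gy as a variation. Section 13.5 is the titled definition and the natural governing rule. What remains is a conflict of terms.

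A reader might also infer radiation delays of up to 6 weeks from the clock. That figure is an arithmetic ceiling. Sites that follow 7.633, 7.634 and 7.365 could not use the later window.

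**Conclusion.** Section 13.2 is wrong as written in two places. The dose-constraint bullet lacks the limit that its neighbour has, and its clock for women without chemotherapy contradicts 7.634. The first creates a risk of undercounting a secondary endpoint. The total cannot be computed from the documents; the per-woman figure of 1/n rests on n being at most 265. The second is a contradiction to correct, with little practical delay expected. The differing use of ineligible is a lesser point, and any bias from it has no fixed direction.

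Two stronger statements should be avoided. One is that conversions will be undercounted: paragraph 1, if applied, would keep these women. The other is that the primary endpoint is unaffected because converters lie outside it. That overlooks women who fail the constraint and decline mastectomy, who appear to fit 16.61 while 13.2 stops their data. The documents do not show that the primary result is materially changed, but they do not support calling it untouched. Severity is minor.

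**What to change.** 1. In 13.2, start the 10-week limit for women without chemotherapy at the last surgery instead of the first planning attempt, as in 7.634.
2. In 13.2, limit the dose-constraint bullet to women who decline mastectomy, as the margin bullet already is, so that converters follow paragraph 1.
3. In 16.62, state that eligibility is judged by 13.5, so that no woman registered before surgery is dropped from the conversion analysis for not receiving a boost, whatever the reason for her conversion.

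The cost is three wording changes, with no change to sample size or analysis method. They do not settle the position of women who fail the constraint and decline mastectomy. The sponsor should decide whether these women belong in the 16.61 set. If they do, ending their data submission is not compatible with the primary analysis, and the cost of following them depends on a number the documents do not give.

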13.3 Discontinuation After Surgery but Prior to Completion of WBI

Patients who discontinue the study after surgery but prior to completion of WBI due to any of the following:

- patient refusal to undergo or complete WBI;
- physician discretion;
- unacceptable toxicity preventing administration/completion of WBI

will go to the observation phase of this trial; that is, they be followed as per the test schedule for 5 years after treatment discontinuation.

Note: Patients who cannot or do not receive boost radiation are ineligible and must discontinue the study. The end of study information should be collected and the patient referred to clinical care.

13.4 Conditions Requiring Study Discontinuation

Patients who discontinue the study at any time due to any of the following:

- patient refusal to continue study tests and/or procedures
- develop disease recurrence
- administration of anti-neoplastic (non-protocol) treatment

will enter the event monitoring phase where disease and vital status will be collected yearly for 5 years after completion of WBI (or treatment discontinuation).

13.5 Definition of Ineligible

A patient is deemed *ineligible* by the data center if, after registration, it is determined that at the time of registration, the patient did not satisfy each and every eligibility criteria for

study entry.

- If the patient did undergo surgery with/without radiation, submit all treatment/intervention forms and the Off Treatment/Cancel Notification Form.
- If the patient did not undergo surgery, submit on-study material and the Off Treatment/Cancel Notification Form. No further data submission is necessary.

Note: If, after a site has registered a patient into the study, the site becomes aware of information that questions the patient's eligibility for the study, the site should contact the QAS/Data Manager at the telephone number and/or email address listed on the Protocol Resources page of the protocol.

13.6 Definition of Cancel

A patient is deemed a *cancel* if she withdrew consent prior to surgery. On-study material and the End of Active Treatment/Cancel Notification Form must be submitted. No further data submission is necessary.

13.7 Recommendations for Local Recurrence

Patients who develop local recurrence are recommended to be evaluated by having a mammogram and MRI and to undergo a mastectomy.

14.0 Biospecimen Submission

14.1 Tissue and Blood Collection Requirements for Correlative Studies

Table 14.1 Summary of Z11102 Tissue and Blood Collection Requirements for Correlative Studies

Biospecimen	Optional/Mandatory	Collection time point	Comment
EDTA whole blood (2 x 10 mL tubes)	Optional	Within 4 weeks after registration	
Frozen tissue specimens¹	Optional¹	Breast conservation surgery	Representative frozen tumor tissue from each site of disease, including positive dissected lymph nodes, if applicable from the first surgery only ²

Biospecimen	Optional/Mandatory	Collection time point	Comment
Formalin fixed, paraffin-embedded (FFPE) tissue blocks¹	Optional¹	Breast conservation surgery or at registration if registering after surgery	If it is not logistically possible to procure, freeze, and ship frozen material, one formalin-fixed paraffin-embedded (FFPE) tissue block from each site of disease, including positive dissected lymph nodes, if applicable, with a corresponding H&E stained slide from each block from the first surgery only^{2,3}

1. For patients registered prior to first surgery either FFPE **OR** frozen tissue specimens will be submitted for patients who consent (both FFPE and frozen are not required). For patients registered after surgery, FFPE specimens should be submitted where available, in patients who consent to the tissue submission.
2. **For the first surgery only in patients consenting to the tissue submission:** when selecting a sample for submission, please choose a block or frozen tumor specimen from **each** site of disease with both the greatest amount/area of invasive breast carcinoma/associated stoma and the least amount of non-invasive mammary epithelium (in situ carcinoma, hyperplastic epithelium, normal epithelium). **Note:** Operative and pathology reports from all surgeries must be submitted. Tissue specimens from subsequent surgeries are **not required** for submission.
3. An alternative submission for FFPE blocks is fifteen 5-micron positive charged slides from **each** site of disease, including dissected, disease-positive lymph nodes, if applicable, with a corresponding H&E stained slide from each block.

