2.3 Correlative Goals

2.31 Comparison of Tissue Protein and Gene Expression Patterns

To evaluate protein and gene expression patterns in tissue taken from each breast lesion and to evaluate the concordance of the findings between these lesions.

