3.14 Foci of Breast Cancer

Upon clinical exam and pre-operative imaging by mammogram +/- MRI, two or three foci of biopsy proven breast cancer separated by ≥ 2 cm of normal breast tissue.

Foci must include *at least one focus of invasive breast carcinoma with another focus of either invasive breast carcinoma or ductal carcinoma in situ (DCIS)*.

No more than 2 quadrants with biopsy proven breast cancer.

Note: The shortest distance between lesions must be reported on mammogram +/- MRI and eligibility criteria must be met on both, if both are obtained.

Note: Patient is eligible for study if lesion is not visualized on all imaging modalities (i.e., any of the lesion(s) is/are visualized on MRI but not on mammogram OR visualized on mammogram but not on MRI). Ultrasound cannot be used to determine patient eligibility; eligibility to be determined by bilateral mammogram +/- MRI **only**. Fine needle aspirate of the second or third lesion to document malignancy is allowed if the first focus is shown to be invasive by core needle biopsy. Patient may remain on study if, upon pathological assessment, two or three lesions identified on pre-operative imaging represent one contiguous lesion.

3.15 Patients may be registered AFTER surgery and PRIOR TO radiation therapy if either of the criteria is met:

1. An area of atypia > 2 cm from the index lesion excised at the time of cancer operation is upgraded to DCIS or invasive carcinoma thereby identifying MIBC.

OR

2. Patient underwent resection of two or three foci of malignancy by breast conservation surgery with a minimum of one invasive focus of breast cancer and a minimum of 2 cm of normal breast tissue between the lesions on final pathology.

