14.22 Optional Tissue Biospecimens

Either frozen (preferred) **or** FFPE tissue specimens from **each** surgical site of disease and a sample of the intervening non-malignant tissue will be submitted for tissue correlative science evaluation and potentially for future research, should the patient consent. Tissue from axillary lymph nodes (sentinel lymph nodes and/or axillary lymph node dissection dependent on case) will also be collected for correlative science evaluation (see Table 14.1.) **A corresponding H&E slide for each submitted block must be provided** to permit quality assessment of each tissue block.

If frozen tissue cannot be provided, the FFPE tissue block is requested. However, **if an institution is unable to provide a tissue block**, cut fifteen

5-micron positive charged slides. **Label the slides with patient study ID number, pathology accession number, and order in which the sections were cut from the block.** H&E stain the first and last five micron slide that is cut (i.e., slides labeled 1 and 15). These H&E slides will be reviewed centrally for assessing tissue quality. The remaining unstained slides will be processed as described in section 14.4. For samples containing less than 7 square millimeters of tumor tissue, multiple sections should be mounted onto each slide to ensure that the appropriate amount of tumor tissue is available. Ideally, each slide must have a minimum of 75 % tumor tissue on the slide to be deemed adequate for study. **Do not bake or place covers slips on the slides.**

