14.33 Tissue Processing and Submission

14.331 Frozen Tissue Processing and Submission

After breast conservation surgery, the specimens should be brought to the pathology department as soon as possible (generally speaking, this means within 15 minutes after the time of tissue resection). **If possible, in order to accurately record the *ex vivo* ischemia time, the time at which the specimens are excised from the patient should be recorded.** The specimens should be kept fresh and not put into any type of fixative, although it may be transported to pathology in a solution of normal saline or any other physiologic buffer. The specimens should be reviewed by the attending pathologist or other

authorized individual (pathology resident, fellow, or qualified pathologist assistant). Material needed for diagnosis should be removed and processed according to the institution's standard procedures. Any remaining tissue may be sent to the Alliance Central Specimen Bank.

Where possible, representative and grossly apparent tumor tissue from each foci of disease and one sample of intervening normal breast tissue should be collected. Where two foci of disease are resected in one lumpectomy, non-malignant tissue from the area between the two tumors should also be submitted. Where two separate foci of disease are resected in separate lumpectomies, non-malignant tissue from the area between the two tumors is ***not required*** to be submitted. Normal tissue from the margin of the lumpectomy specimen can be submitted as the intervening normal tissue. Tissue that is grossly necrotic, hemorrhagic or cauterized should be avoided. Tissue should be rapidly divided into segments no larger than 1 cm³ (1 gram). As many as possible (but at least one) of these sized segments should be collected from each site of disease.

If the foci are removed separately and margins on both are negative, it is assumed that the radiographic distance (closest distance by MRI or mammogram) would be the appropriate separation.

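### The tissue-selection rule in Table 14.1 lists in situ carcinoma among the tissue to minimise, so for an eligible DCIS-only focus it steers sites away from the blocks richest in the lesion under study

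*Combined protocol and SAP*

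**What the plan says.** **Selection rule.** Footnote 2 of Table 14.1 is attached to both the frozen and the FFPE rows. It applies one rule to every site of disease: choose the specimen "with both the greatest amount/area of invasive breast carcinoma/associated stoma and the least amount of non-invasive mammary epithelium". A parenthesis spells out the tissue to be minimised: "in situ carcinoma, hyperplastic epithelium, normal epithelium".

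**Eligibility.** Section 3.14 requires "at least one focus of invasive breast carcinoma with another focus of either invasive breast carcinoma or ductal carcinoma in situ (DCIS". Section 3.15 also lets a woman register after surgery when an area of atypia "is upgraded to DCIS or invasive carcinoma thereby identifying MIBC". A focus that is DCIS only is therefore eligible by either route.

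**Purpose of the tissue.** Goal 2.31 is to study protein and gene expression in each lesion and "to evaluate the concordance of the findings between these lesions". Section 14.42 takes DNA and RNA from each tumor site. It calls a pair related if the genomic features are similar and unrelated if they are discordant.

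**Other collection instructions.** The frozen row of Table 14.1 asks for representative tumor from each site. Section 14.331 asks, where possible, for "representative and grossly apparent tumor tissue from each foci of disease". Section 14.332 asks for FFPE material from every malignant focus. Section 14.22 adds, for slides: "Ideally, each slide must have a minimum of 75 % tumor tissue on the slide to be deemed adequate for study".

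**The concern.** The rule suits an invasive focus, where surrounding in situ or benign epithelium dilutes the tissue of interest. It does not carry over to a focus that is entirely DCIS, because there the in situ carcinoma is the tissue of interest. Section 7.2 itself counts DCIS as part of the tumor bed.

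At stake is the comparison within pairs. If the DCIS member of an invasive/DCIS pair arrives with little tumor, either it fails quality assessment and the pair is lost, or it is assayed at low tumor content and the call is less reliable. Section 14.42 states no minimum tumor content for calling a pair related or unrelated. Any loss would fall on one identifiable subgroup, women whose second focus is DCIS. It would therefore affect both the concordance estimate and the exploratory contrast of local recurrence between related and unrelated tumors.

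**Working it through.** The plan gives no figure to reproduce here, and no sample-size or power calculation enters. The check is to apply footnote 2 literally to a focus with no invasive component, and then to look for an exception elsewhere.

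**Step 1: what the rule can act on.** In a DCIS-only focus the invasive area is 0 in every block, so the first criterion ties. Only the second criterion, least non-invasive epithelium, separates the blocks. Write *d* for the share of a block that is DCIS and *b* for the share that is hyperplastic or normal epithelium. The rule then picks the block with the smallest *d + b*.

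**Step 2: direction.** Block A is preferred to block B when *d_A + b_A < d_B + b_B*, that is, when *d_A − d_B < b_B − b_A*. At equal benign epithelium the rule always takes the block with less DCIS. A block with more DCIS wins only if its shortfall in benign epithelium exceeds its excess of DCIS.

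**Step 3: two examples (all block contents are assumed).**

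| | Block A | Block B | Rule picks |
|---|---|---|---|
| Example 1 | 60 % DCIS + 5 % normal = 65 % | 5 % DCIS + 10 % normal = 15 % | B, with less DCIS |
| Example 2 | 30 % DCIS + 0 % normal = 30 % | 10 % DCIS + 40 % normal = 50 % | A, with more DCIS |

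In Example 1 the chosen block is 75 − 5 = 70 percentage points below the slide ideal in Section 14.22, and the rejected block is 75 − 60 = 15 points below it. Example 2 shows that pooling DCIS with benign epithelium can also give the desired choice. The rule therefore penalises DCIS but does not always pick the block with least tumor.

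**Step 4: search for an exception.** Sections 2.31, 3.14, 3.15, 7.2, 7.3 and 14.1 to 14.4 contain none for a focus without an invasive component. Sections 14.331 and 14.332 say to send tissue from each focus. For FFPE, only footnote 2 says which block to send.

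**Step 5: can a poor choice be repaired later?** Section 14.22 has several sections mounted per slide when there is less than 7 square millimeters of tumor. That adds tumor area but leaves the tumor fraction unchanged. The H&E slides can reveal a poor block. However, Table 14.1 asks for one FFPE block per site, from the first surgery only, and Section 14 describes no resubmission.

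**Step 6: the proposed wording on the same examples.** Choosing the greatest *d* and the least *b* selects block A both times (60 % and 5 % against 5 % and 10 %; 30 % and 0 % against 10 % and 40 %).

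**The case against.** The strongest reply is that footnote 2 should not be read alone. It refines table rows that already ask for tumor from each site, and Sections 14.331 and 14.332 repeat that request. A pathologist facing a DCIS-only focus would see that the invasive criterion has nothing to act on and would send DCIS. An H&E slide must accompany each block for quality assessment, scant tumor has its own provision, and full-genome sequencing is limited to patients with good frozen samples from each tumor site. Tissue submission is optional, and Section 14.42 declares all of these statistics exploratory. Section 16.51 stops the trial if more than 8 local recurrences occur as first events, so the related/unrelated recurrence contrast would rest on few events in any case.

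Much of this stands. It limits the consequence and rules out several stronger readings:

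- **That the rule always selects the block with least tumor.** It does not, because DCIS is pooled with hyperplastic and normal epithelium (Example 2).
- **That invasive/DCIS pairs cannot be compared.** This does not follow. Tissue from each focus is still requested, and the H&E slides allow a poor sample to be recognised.
- **That these pairs would be systematically miscalled as unrelated.** A quality failure gives missing data, not a wrong call. A wrong call needs a poor sample to pass review and its low tumor content to be ignored. Section 14.42 also plans to compare mutation frequencies, not just lists of mutations.
- **That the frozen route would miss DCIS because it is not grossly visible.** The documents do not say how often that happens, and FFPE is already the fallback when frozen tissue cannot be provided.

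The reply does not remove the contradiction. A site that follows the written selection rule and a site that follows the general request for tumor may send different blocks, and the plan does not say which instruction prevails.

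**Conclusion.** The point holds in a limited form. Footnote 2 is a stated rule that misfires for an eligible type of focus, and it conflicts with neighbouring instructions. The supported consequence is a risk of low tumor content in DCIS-only foci, and hence of lost or unreliable invasive/DCIS pairs in the concordance work.

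Its size cannot be calculated. The documents do not give the share of women with a DCIS-only focus, the number who will consent to tissue submission, or the tumor content of the blocks that would be chosen. A percentage shift in the proportion called related would only restate assumed inputs. The conclusion also assumes that sites apply the footnote literally and have more than one candidate block or specimen for the focus; with only one there is nothing to select.

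The primary local-recurrence analysis does not use this tissue and is unaffected. The change is worth making because it is cheap and serves a stated goal.

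**What to change.** 1. Add one sentence to footnote 2 of Table 14.1: for a focus with no invasive component, choose the block or frozen specimen with the greatest area of DCIS and the least hyperplastic and normal epithelium.
2. Record whether each submitted focus is invasive or DCIS. Pathology reports from all surgeries are already required by footnote 2, and Section 18.2 already collects biopsy and pathology information, so this mainly means linking existing information to the specimen.
3. State in Section 14.42 that concordance will be reported separately for invasive-invasive and invasive-DCIS pairs.

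The cost is a few sentences and one data item, with no change to patient care, accrual or the primary analysis. A compulsory move from frozen to FFPE for DCIS foci is not proposed. It could mix specimen types within a pair, and Section 14.42 reserves its deepest genomic analysis for patients with a frozen specimen from each tumor.
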